# Administrative Information

## 1. Title

Project SUPPORT (**Socio-legal Services for Underserved Populations Through Patient Navigation to Optimize Resources During Treatment**)

## 2. Trial Registration

Clinicaltrials.gov identifying number: NCT02232074

## 3. Protocol

Version 5: 9/1/2017

## 4. Funding IRB

This study has been approved by the Boston University Medical Center Institutional Review Board. IRB #: H-32599

Funding for Project SUPPORT is provided by: Patient Center Outcomes Research Institute ([www.PCORI.org](http://www.PCORI.org) AD-1304-6272) and the American Cancer Society ([www.cancer.org](http://www.cancer.org) ACS 124014-RSG-13-368-01-CPPB )

**PI:** Principal Investigator, **RA:** Research Assistant, **MLPB:** formerly known as Medical Legal Partnership | Boston **PN:** Patient Navigator, **BMC:** Boston Medical Center, **BUSPH:** Boston University School of Public Health

**Scientific Steering Committee:**

- a. Comprised of the study key personnel and 2 additional investigators at Boston Medical Center with expertise in cancer and community health interventions:
- b. This committee consults with the research team guide the methodology, data collection, analyses, and dissemination activities throughout the course of the study.
- c. Scientific Steering Committee meetings are held a minimum of four (quarterly) and a maximum of six (bimonthly) times per year.

**Patient Advisory Group:**

This committee serves as a formal communication vehicle for patients to take an active role in decisions related to the research design, study implementation, and dissemination activities.

- a. Each member of the Patient Advisory Group brings an individual experience of cancer treatment, survivorship, and talents. As the project evolves, division into separate working groups such as dissemination and outreach will provide an opportunity for these talents to be best represented.

- b. Each advisory group meeting will include a discussion of current and future dissemination activities that will be designed by the patients but supported and executed by program staff.
  
- c. Patient Advisory Group meetings are held a minimum of four (quarterly) and a maximum of six (bimonthly) times per year. The Patient Advisory Group is also invited to participate in the quarterly (4 times per year) Community Advisory Board meetings.

# Introduction

## 6. Background and Rationale

**Cancer inflicts a substantial toll on society with a disproportionate burden borne by minority and low income populations.** Prevalence of cancer in the US was estimated at 15,112,198 cases in 2015 with 1,735,350 new cases in 2018 (1, 2). Cancer remains the second leading cause of death in the US, accounting for over 598,030 deaths in 2016 (3) Since the year 2000, cancer mortality surpassed heart disease as the leading cause of death in women aged 40–79 and men aged 60–79 (4). Breast, lung and bronchus, and prostate cancer account for the highest mortality rates nationwide (1, 5). It has long been recognized that the burden of cancer falls disproportionately on people of color (6). Both incidence and mortality are elevated among minorities, especially Blacks, who are more likely to be diagnosed with certain cancers, to be diagnosed at advanced stage, and to die from the disease (7). Evidence is clear, though, that race and ethnicity are closely related to socioeconomic status (SES), so many racial/ethnic disparities are associated with differences in income, education and health insurance coverage (8). Studies consistently show that the cancer burden increases as income, insurance status and educational attainment decline,(1, 9-11) regardless of race/ethnicity.

**Cancer health disparities are growing despite ongoing advances in scientific discovery.** While overall cancer mortality rates continue to decline, not all segments of the US population benefit equally from this progress (12). Death rates in those with lower SES, as defined by education, occupation, or residence, have shown little or no decrease, and even increased in some instances (7, 13, 14). Any decrease in cancer death rates among minorities has occurred later and has been slower compared to Whites. As a result, the gap in mortality rates between advantaged and disadvantaged segments of the US population has continued to widen (7, 13, 14). For instance, cancer death rates for men in 1993 were two times higher in the least educated compared to the most educated groups, but by 2007 this mortality difference had increased to nearly three-fold (7). Despite continued advancement in early detection and targeted treatments for women with breast cancer, Black women continue to die from breast cancer at a higher rate than their White counterparts (7).

**Social determinants of health create obstacles in obtaining timely, quality care and are one of the underlying causes for existing cancer disparities.** While the interplay of race, poverty and other socioeconomic indicators on cancer outcomes is complex, research has clearly documented the impact that barriers to accessing cancer care have on patient outcomes, regardless of race/ethnicity (13-16). One primary cause of cancer disparities among lower SES populations is the presence of financial, structural, and personal barriers to health care, including inadequate health insurance, lower literacy, and reduced access to recommended preventive care and treatment service (1). These obstacles to cancer services create documented delays in care and are increasingly scrutinized as a source of poor survival for many vulnerable populations,(17-26) while large population-based studies find that equal high quality treatment can significantly reduce disparities in mortality (27). **Thus, evidence-based interventions to reduce delays in care resulting from social barriers or obstacles are needed to reduce disparities in cancer outcomes.**

**Patient navigation represents a promising remedy to reduce cancer disparities by intervening to address barriers to timely care.** Navigation is a patient-centered care coordination model that uses lay health workers who are integrated into the healthcare team to support disadvantaged patients for a

defined episode of cancer-related care (28-30). The specific goal of navigation is to reduce delays in care by identifying and addressing patient barriers to care. Our research team at Boston Medical Center (BMC) pioneered the development of a lay patient navigation model supporting low income minority patients that demonstrated significant impact on timely care (31-36) and contributed to widespread dissemination of navigation as a current standard in cancer care (6, 37). Patient navigators are trained to work closely with patients and providers to identify individual patient obstacles to care (38, 39) and then link patients to existing loco-regional resources to overcome them. Barriers documented most frequently include: communication issues, scheduling issues and socio-cultural issues such as fear or mistrust. Patient navigators helped reduce missed appointments by 50% and also decreased time to screening and diagnosis (31, 33, 34).

To facilitate discussion on how to improve navigation services for patients with cancer, the National Cancer Policy Forum of the National Academies of Sciences, Engineering, and Medicine held a workshop on Establishing Effective Patient Navigation Programs in Oncology in Washington, DC, on November 13 and 14, 2017. At this workshop, a broad range of experts, including clinicians, navigators, researchers, and patients, provided an overview of patient navigation, explored current models of patient navigation programs, identified lessons learned from implementation of patient navigation programs as well as gaps in the evidence base, including the need for comparative effectiveness studies to inform best practices (40).

**In the years leading up to our study design process and proposal submission**, preliminary studies by our research team suggested that the presence of barriers, particularly certain **socio-legal barriers**, contribute to persistent delays in care despite navigation. We defined **socio-legal barriers** as social problems related to meeting life's most basic needs that are addressed by existing public policy, law, regulation and programming and are thus potentially remedied through legal advocacy/action (41). (Over time, socio-legal barriers may become understood as part of (or even subsumed) by the broader category of Social Determinants of Health (SDOH), a concept whose taxonomy is still young in the domain of academic medicine.

Indeed, while Project SUPPORT was conceptualized in 2011-13, it was not until May 2017 that CMS published for the first time on the topic of "health-related social needs": <https://nam.edu/wp-content/uploads/2017/05/Standardized-Screening-for-Health-Related-Social-Needs-in-Clinical-Settings.pdf>.) Project SUPPORT was grounded in MLPB's experience that social needs have a legal dimension (a) to the extent that a patient has sought resources or assistance from an agency/authority (perhaps with the encouragement and help of a patient navigator) and has been denied that support, possibly in violation of the patient's legal rights, or (b) the patient and navigator are aware of the unmet social need but not aware that they have legal rights, or if they are aware -- how to exercise them effectively.

Unmet essential needs that often involve socio-legal barriers are reflected in the acronym **I-HELP** initially published in *Pediatrics* in October 2007: **I**ncome supports & Insurance; **H**ousing & Utilities; **E**mployment & Education; **L**egal Status; **P**ersonal & Family Stability/Safety (42). Each category reflects basic life needs that, if not met, may affect health and may be amenable to direct legal advocacy or service intervention should initial efforts by patients/families to satisfy these needs be unsuccessful.

Data from the National Patient Navigation Research Program (PNRP), the largest multi-site study of navigation in cancer care to date, documents the impact socio-legal barriers have on equitable cancer

care. Using a list of 20 discrete barriers to care (43), PNRP navigators were also trained to document reported patient barriers to care during each patient encounter.

Analyses found that navigated patients with documented barriers to care experience less timely resolution of their screening abnormalities; the more barriers present, the less timely their care (44). In a secondary analysis, we categorized barriers into two groups: 1) socio-legal barriers and 2) other barriers. Among 1,493 patients receiving navigation, only 6% had socio-legal barriers to care documented by the navigator. The top 3 barriers documented by navigators were: language issues (25%), scheduling issues (14%), and fear (12%). Yet, those with socio-legal barriers to care were less likely to have timely resolution of diagnostic care (aHR: 0.51, 95% CI: 0.39, 0.66) compared to those with other barriers, even when accounting for the presence of multiple barriers. This is one of the most robust findings in the Boston PNRP dataset, and a stronger predictor of delay in treatment than insurance status or race and ethnicity (45).

These findings are supported by other navigation studies that report outcomes are limited by housing, insurance and financial needs (46-48). **Therefore, it makes sense that navigation had only a modest effect in our low-income population in prior navigation studies, as navigators were not trained to identify or address these complex socio-legal barriers to care with remedies external to the healthcare system.**

**Research demonstrating the impacts of integrating legal support into patient care – exemplified by the medical-legal partnership approach -- is only beginning to emerge**, but much more needs to be known regarding the size of effects (15, 41, 49, 50). Current legal reports document improvements in self-reported health, including feeling more empowered after receiving MLPB services (50), having reduced stress (49), and improvement in one's general health (15).

A retrospective study of patients in palliative care found that 297 referrals made to an MLPB program from 2004 through 2007 addressed patients' legal needs, from reinstating food stamp benefits, to executing last wills and testaments (51). A pilot study of an MLPB tailored for pediatric patients found the proportion of families who accessed food and income supports significantly increased, while the proportion of families who avoided medical care due to perceived cost and insurance barriers significantly decreased (15). In a pilot study of 20 cancer patients who received legal services, 75% said the legal services reduced stress and 45% reported a positive impact on their financial situation, 30% said the services helped them maintain their treatment regimen, and 25% said legal services helped them keep medical appointments (52). **However, rigorous research demonstrating the impact of legal support for disadvantaged populations on timeliness of care in general, and of cancer care in particular, are lacking, representing a critical gap in the science of cancer disparities.**

Project SUPPORT (**S**ocio-legal services for **U**nderserved **P**opulations through **P**atient Navigation to **O**ptimize **R**esources during **T**reatment) is an innovative, patient-centered intervention that was designed in partnership with a diverse group of community stakeholders to address persistent cancer care disparities for vulnerable cancer patients seeking services at an inner-city safety net hospital. We utilize Community-Engaged Research methods to design, implement and evaluate a comparative effectiveness care delivery randomized controlled trial for a racially/ethnically diverse, low income population with newly diagnosed cancer.

We hypothesize that compared to standard navigation, a navigation intervention supported by legal advocacy will address patient-reported socio-legal barriers and lead to delivery of equitable cancer care. Our specific aims are to measure the impact of a **legal support-enhanced patient navigation** intervention on:

- 1) Clinically relevant outcomes: receipt of timely and quality cancer care.
- 2) Patient-reported outcomes: distress, needs and satisfaction.
- 3) Intermediate outcomes: *socio-legal barriers to cancer care*.

## 7. Objectives

**Research Question:** Compared to standard patient navigation, will a more patient-centered navigation intervention in partnership with the MLPB (formerly known as Medical Legal Partnership | Boston) that identifies and addresses socio-legal barriers to care in newly diagnosed cancer patients seeking care in an urban safety-net result in: 1) improvements in patient-reported distress, perceived needs, self-efficacy and satisfaction with the navigator, 2) more timely and better quality care, and 3) elimination of patient-reported socio-legal barriers to care?

**Hypothesis:** compared to standard navigation a navigation intervention supported by legal advocacy will address patient-reported socio-legal barriers and lead to delivery of equitable cancer care

## 8. Trial Design

Randomized controlled trial

- N= 374 newly diagnosed breast & lung cancer patients
- 187= Control (standard navigation)
- 187= Intervention (MLPB enhanced navigation)

## Methods

### 9. Study Setting

Boston Medical Center

Study participants will be identified by screening recently diagnosed breast and lung cancer patients presenting for care Boston Medical Center. Eligible patients will be identified using 3 sources (pathology reports, referrals and weekly multidisciplinary tumor board conference

### 10. Eligibility

All patients must meet the following criteria in order to participate in project SUPPORT:

#### Eligibility criteria:

- Newly diagnosed lung or female breast cancer
- 18 years or older
- Receiving cancer treatment at Boston Medical Center
- English, Spanish or Haitian Creole speaking
- Patient is eligible within one month (30 days or less) of being notified of her/his cancer diagnosis.

#### Exclusion criteria include:

- Patient informed of cancer diagnosis >30 days
- Patient under 18 yrs. of age
- Primary language something other than English, Spanish or Haitian Creole
- Undergoing treatment for concurrent cancer
- Male breast cancer patients
- Patient has history of cancer or has received cancer treatment within the last 5 years
- Institutionalized/cognitive impairment such as: dementia or metabolic, medication or drug induced, psychosis (given the unique challenges to their treatment decision making/adherence and the fact that the intervention would not include the patient directly, but rather the family).
- Small Cell Lung Cancer type

## 11. Intervention

### Control arm: Standard Patient Navigation

- a. Current standard of care for cancer patients at BMC
- b. Patient Navigators (PN) complete navigation training through the Oncology Department
- c. PN follows the Care Management Model
  - i. Case identification
  - ii. Barrier identification
  - iii. Care plans to address identified barriers
  - iv. Long term tracking

### Intervention arm: MLPB-enhanced patient navigation

- a. Intervention Patient Navigator (IPN) has had standard of care patient navigation training through the Oncology Department
- b. IPN interactions with patients are documented by the IPN in the Oncology Navigator template in the EMR
- c. Navigator has also completed MLPB orientation and training
  - i. Focusing on 3 areas:
    1. Housing
    2. Employment
    3. Disability
  - ii. Additional trainings will cover study specific protocol and procedures:
    1. protocol implementation & documentation
    2. administering detailed legal screen/facilitation questions
    3. present information/consult to MLPB
  - iii. MLPB training curriculum includes: social determinants of health, range of available legal remedies, needs assessment through comprehensive screening, developing and implementing care plan through legal triage consultation
  - iv. The Intervention PN (IPN) will administer a **Detailed Legal Screen** to all study participants randomized to the intervention group within the first week of study enrollment and again at 3 months post-enrollment
  - v. Once an initial **Detailed Legal Screen** is completed with the participant, IPN will contact MLPB to discuss the participant's responses to the screen
  - vi. MLPB documents decisions on **Level of Legal Need** form.

## Level of Legal Need Coding

Outcome	Level of need	Action
Non-legal issue	0	Facts conveyed by patient to PN, and PN to MLPB, do not reflect that patient has a legal risk/need (as opposed to some other type of need).
Basic legal issue	1	Facts conveyed by patient to PN, and PN to MLPB, reflect that patient has a legal risk/need, but one that can be addressed through MLPB sharing referral recommendations and/or simple information via a single interaction between MLPB and PN (for transmittal to the patient by PN, as appropriate). No follow-up consultation between MLPB and PN is expected or planned.
Intermediate legal issue	2	Facts conveyed by patient to PN, and PN to MLPB, reflect that patient has a legal risk/need, addressing of which will involve multiple consultations between PN and MLPB re: available strategies - contemplates an ongoing advocacy coaching interaction.
Complex legal issue	3	Facts conveyed by patient to PN, and PN to MLPB, reflect that patient has a more complex legal risk/need, so, depending on the nature of the issue and the timing, MLPB either will: 
 
(a) provide pro se advice and counsel to patient;
 
(b) refer patient to a specialized resource for free legal assistance; or
 
(c) schedule patient for an MLPB legal intake interview.
 

Out of MLPB scope issue	9	Facts conveyed by patient to PN, and PN to MLPB reflect that patient has a legal risk/need that is outside the scope of MLPB coverage for this study (such as a criminal law, immigration law, or personal and family safety & stability law issue); MLPB provides readily available referral information only.

## 11.1 Participant Withdrawal

When a participant expresses interest in withdrawing from Project SUPPORT, the RA should try to ascertain and document the reasons why the participant has chosen to withdraw and what study components, if any, the participant is willing to continue participating in.

### Information needed to document withdrawal in REDCap project

Whether withdrawal was a result of decision made by participant or investigator

- 1) Reason(s) for withdrawal, if known
- 2) Whether withdrawal was from all components of research study or just the primary interventional component
- 3) Date of withdrawal
- 4) Did confirmation of withdrawal occur over the phone or in person

## 12. Outcomes

### 12.1 Primary Outcomes

#### Time to first treatment

- 1) **Timely initiation of care:** The receipt of timely care will be defined as initiation of care within 90 days, as this the shortest delay that has been shown to consistently affect mortality and categorized as a dichotomous variable (yes/no). The time element will be calculated from date of diagnosis (Time 0) to date of treatment initiation (Time 1). The date chosen for the Time 1 variable will depend on the recommend care plan for each patient, as derived from the chart abstraction and based on patient presentation, including but not limited to stage at diagnosis and co-morbid medical conditions. In all cases Time 1 will be defined as the date of the first treatment **after** patient has received a definitive cancer diagnosis.
- 2) **Time to initiation of care:** continuous outcome defined as the number days from diagnosis (Time 0) to treatment initiation (Time 1).
- 3) **Rate of missed appointments:** percent of scheduled appointments that are missed over 12 month period.
- 4) **Quality of care:** Dichotomous variable (Y/N) based on select measures of quality care, as developed jointly by the Commission on Cancer, NCCN and American Society of Clinical Oncology
  - a. Measured using data abstracted from medical chart

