## 14. Sample Size

Sample size estimates for the clinically relevant outcomes are based on the primary metric: **timely initiation of primary treatment**, a dichotomous outcome (yes/no) calculated for each subject. Since clinical outcomes will be derived from the medical record, we do not anticipate any loss to follow up on these outcomes. We anticipate our study will have 80% power of detecting an advantage to navigation enhanced by a medical-legal partnership, if the enhanced intervention raises the percent in each group receiving timely initiation of care from 76% to 90.5% (testing at the two-tailed .05 level) from patient navigation alone to legal navigation. Comparison of the two study groups on our secondary outcome of time to initiation of cancer treatment, or the number of days to the start of treatment, through survival analysis, takes advantage of more information and should provide somewhat greater power. For example, given the above scenario, (76% vs. 90.5% initiation of care by 90 days) and assuming a constant hazard, (i.e., exponential survival), a log rank test gives 86% power of detecting a difference between the two study groups.

Second, we will conduct separate analyses for the breast and lung cancer participants.

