### **Analysis**

**Primary Clinical Outcomes: To measure the impact of patient navigation enhanced by MLPB intervention on *receipt of timely and quality cancer care*:**

- Our primary analysis will use multiple logistic regression models to compare the proportion of patients with *timely initiation of treatment* across study groups, adjusting for the influence of race/ethnicity (white vs non-white), cancer site, insurance status (private vs public), and other covariates that may have a significant effect on the outcome and may be unbalanced across the two study groups.
- Study groups will also be compared on the secondary clinical outcome of *time to initiation of primary cancer treatment* (the number of days from diagnosis to start of treatment) through Kaplan-Meier survival curves (unadjusted analyses) and Cox proportional hazards regression models controlling for cancer site and other covariates (adjusted analysis).
- *Receipt of quality care* for each cancer type will be analyzed through logistic regression.
- For the analysis of the rate of missed appointments, patients will differ on the number of scheduled appointments over the study period. We will generate summary measures of the rate and total numbers of missed appointment for the total study cohort and by treatment group.
- The primary analysis will include only participants who have legal issues at baseline (defined by the results of their baseline I-HELP general legal screen, which will take place within one month of new diagnosis). This will be the official sample of patients which the sample size calculations are based (n=117 in each group adjusting for 10% dropout).

**Secondary outcomes: To measure the impact of patient navigation enhanced by MLPB intervention on patient-reported outcomes: *distress, needs, and satisfaction*:**

- Patient-reported outcomes will be measured at baseline, 3 month follow-up, 6 month follow-up, and 12 months using summation scores with established subscales.
- Multiple linear regression models controlling for baseline levels of the outcome (i.e., analysis of covariance models) will be used to compare study groups on changes in *distress* and *psychosocial needs* at follow-up. Multiple linear regression models will also examine intervention effects on *satisfaction* scores.

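### Section 12.1 lists four primary outcomes, but Sections 14 and 20 size and analyse the trial on timely initiation alone and call time to initiation secondary

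*Protocol*

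**What the plan says.** Under the heading "12.1 Primary Outcomes", the protocol numbers four outcomes without ranking them: (1) timely initiation of care within 90 days, yes or no; (2) time to initiation, a "continuous outcome defined as the number days from diagnosis (Time 0) to treatment initiation (Time 1"; (3) the rate of missed appointments over 12 months; (4) quality of care, yes or no. Section 12.2 is a separate secondary list, made up of patient-reported measures. Time to initiation is not on it.

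Section 14 opens with "Sample size estimates for the clinically relevant outcomes are based on the primary metric" and identifies that metric as timely initiation, tested two-sided at 0.05 with 80% power. It then continues: "Comparison of the two study groups on our secondary outcome of time to initiation of cancer treatment".

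Section 20 gathers the clinical outcomes under a heading that begins "Primary Clinical Outcomes: To measure the impact of patient navigation enhanced by MLPB intervention on". Within that block, timely initiation receives the primary analysis: "Our primary analysis will use multiple logistic regression models to compare the proportion of patients with" timely initiation. Time to initiation is introduced with "Study groups will also be compared on the secondary clinical outcome of" and analysed by Kaplan-Meier curves and Cox regression. Quality of care gets logistic regression, and missed appointments get summary measures overall and by group. The analysis set for the primary analysis is given as "n=117 in each group adjusting for 10% dropout".

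**The concern.** The section that formally defines the outcomes and the sections that size and analyse them do not agree. Time to initiation is primary in Section 12.1 and secondary in Sections 14 and 20. Missed appointments and quality of care are primary in Section 12.1 and fall under the primary heading of Section 20, but no sizing is given for them and no part of the 0.05 is set aside for them.

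At stake is the claim that the trial can make. Suppose the 90-day comparison is not significant but the analysis of days to treatment, or of quality of care, is. A report that follows Section 12.1 could then say that a primary outcome was met. A report that follows Sections 14 and 20 could not. The protocol should not leave that choice open until the results are known.

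**Working it through.** **Step 1. The status of each outcome, section by section.**

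| Outcome | Section 12.1 | Section 14 | Section 20 |
|---|---|---|---|
| Timely initiation, 90 days | primary | the primary metric; sized | the primary analysis |
| Time to initiation | primary | secondary; a power figure only | secondary, under a primary heading |
| Missed appointments | primary | not mentioned | under the primary heading; no rank of its own |
| Quality of care | primary | not mentioned | under the primary heading; no rank of its own |

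Only the second row is a direct contradiction. In the last two rows the label has no sizing or alpha behind it.

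**Step 2. Does the stated size rest on timely initiation alone?** Inputs from Section 14: p1 = 0.76, p2 = 0.905, two-sided alpha 0.05 (z = 1.960), power 80% (z = 0.842). From Section 20: 117 per group, 10% dropout.

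Pooled-variance formula: n = [1.960·√(2·p̄·(1−p̄)) + 0.842·√(p1(1−p1) + p2(1−p2))]² / (p2−p1)².

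- p̄ = (0.76 + 0.905)/2 = 0.8325, so 2·p̄·(1−p̄) = 0.2789.
- p1(1−p1) + p2(1−p2) = 0.1824 + 0.0860 = 0.2684.
- n = [1.960·0.5281 + 0.842·0.5181]² / 0.145² = 102.9, so 103 per arm.
- Allowing for 10% dropout: 103/0.9 = 114.4, so 115 per arm.
- With a continuity correction and no dropout allowance: 116.3, so 117 per arm.

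Power of the uncorrected test is 0.81 at 105 evaluable per arm (117 × 0.9 = 105.3) and 0.85 at 117. The stated 117 is thus reproduced exactly by one route and within 2 per arm by the other. Both routes give the whole two-sided 0.05 to timely initiation, and nothing is reserved for the other three outcomes.

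**Step 3. Conditional illustration: what if either timing outcome could be claimed as a met primary at 0.05?** The two outcomes come from the same dates and are correlated, so the chance of at least one false positive lies between 5% (complete overlap) and 1 − 0.95² = 9.75% (independence). It was simulated under these assumptions:

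- exponential times, as in Section 14;
- the same 90-day rate in both arms, set at 76%, 83% or 90.5%;
- 105 or 117 per arm;
- log-rank follow-up of 90, 180 or 365 days (assumed; the protocol gives no censoring time);
- an unadjusted two-proportion test at 90 days and a log-rank test, each at two-sided 0.05;
- 20,000 trials per setting (Monte Carlo standard error about 0.002).

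The chance that at least one test was significant was 0.069 to 0.086, or about 7-9%.

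**The case against.** The best defence is that primary in Section 12.1 names a domain, not a rank. Sections 12.1 and 12.2 divide clinical outcomes from patient-reported ones, in line with the first two specific aims. Section 20 itself calls one item secondary beneath a primary heading, which makes sense only if the heading names a domain. Sections 14 and 20 also agree on one powered outcome and one primary analysis, so the intended hierarchy can be worked out.

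Much of this stands. The intention is recoverable, and that is why the remedy is clear and the powered analysis is not in question. But the defence does not remove the conflict. Section 12 is where the outcomes are defined, its separate secondary list omits time to initiation, and no sentence says that primary means clinical. Missed appointments and quality of care are nowhere called secondary, so a reader cannot demote them from the text. Nor is this detail that an analysis plan would supply, because the protocol itself gives one outcome two ranks.

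Three stronger readings are tempting and are not supported:

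- A reader might infer that the plan as written has an inflated error rate. It does not follow, because no rule says that success on any one listed outcome is enough.
- A reader might compound several tests as if they were independent. The two timing outcomes share the same data, so that overstates the risk.
- A reader might fault the summaries promised for missed appointments as a missing model. The outcome is already defined as a percentage of scheduled appointments, and the choice of a between-arm model is commonly left to an analysis plan, which is not at hand.

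**Conclusion.** The inconsistency is real and should be fixed. Time to initiation is primary in Section 12.1 and secondary in Sections 14 and 20, which follows directly from the text and needs no assumption. Missed appointments and quality of care are not contradicted in the same way: they are labelled primary without sizing or alpha to support the label.

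The size and power statement supports a single primary outcome, timely initiation within 90 days, and its arithmetic holds up. The figure of about 7-9% applies only if either timing outcome were allowed to count as a met primary. It rests on exponential times, assumed follow-up and unadjusted tests, whereas the written primary analysis is a covariate-adjusted logistic regression. It shows why the label matters; it is not a property of the plan.

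**What to change.** In Section 12.1, name timely initiation of care within 90 days as the single primary outcome, as Sections 14 and 20 already treat it. Move time to initiation, missed appointments and quality of care to the secondary outcomes. Alternatively, if confirmatory claims on them are wanted, state a fixed order in which they are tested after timely initiation, each only if the one before it is significant. Change the Section 20 heading so that it no longer presents all four as primary.

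The cost is a wording change, and three outcomes lose the primary label. The sample size, the alpha and the primary analysis stay as they are.
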